8.2.2 Duration of Response (DoR)

DoR is defined as the time in months from date of the first documentation of objective response (CR or PR) to the first documentation of objective PD or to death due to any cause in the absence of documented PD (i.e., min (PD date, death date) – date of the first observation of response +1). DoR will only be calculated for the subgroup of patients achieving a confirmed CR or PR.

$$DOR = (\text{Min}(PD \text{ Date}, \text{Death Date}) - \text{Date of the First Observation of Response} + 1)/30.4375$$

8.2.3 Clinical Benefit Rate (CBR)

CBR will be categorized in accordance with RECIST v1.1. CBR is defined as the proportion of patients documented to have a confirmed CR or PR, or SD.

8.2.4 Progression-Free Survival (PFS)

PFS is defined as the time from the first dose of study drug to the date of PD or death due to any cause in the absence of documented PD, whichever occurs first.

$$PFS \text{ (in months)} = (\text{First Event Date} - \text{First Dose Date} + 1)/30.4375.$$

8.2.5 Overall Survival (OS)

OS is defined as the time from first dose of study drug to the date of death due to any cause.

$$OS \text{ (in months)} = (\text{Date of Death} - \text{Date of First Dose of Study Drug} + 1)/30.4375.$$

8.3 Study Drug Exposure Variables

The term study drug in the exposure definitions below, refers to Glesatinib and Sitravatinib unless otherwise specified.

8.3.1 Study Treatment Duration

Study treatment duration will be summarized separately for each study drug and Nivolumab and is defined as;

- Study Treatment Duration (weeks) = $(\text{Last Dose Date} - \text{First Dose Date} + 1)/7$.

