6.1 Lead-in Dose Escalation Evaluation

The study will begin with a lead-in phase dose escalation evaluation of two dose levels of each investigational agent in combination with Nivolumab, in cohorts of 3 to 8 CIT-experienced patients each. Table 5 lists the planned dose levels for each agent, with the starting dose for each agent shown as Dose Level 1.

Patients may be escalated to Dose Level 2 or de-escalated to Dose Level -1, depending on safety observations.

Table 5: Investigational Study Drug Starting Dose Levels for Cohorts of Patients in the Lead-In Phase Dose Evaluation

Drug	Regimen	Dose Level		
		1	2	-1
Glesatinib Tablets	Twice Daily	500 mg	750 mg	350 mg
Sitravatinib Capsules	Once Daily	120 mg	150 mg	80 mg
Mocetinostat Capsules	Three Times Weekly	70 mg	90 mg	50 mg

Depending on experience in early cohorts of patients in the lead-in phase dose escalation evaluation, doses below those shown in Table 5 may be implemented in subsequent cohorts of patients after discussion among Investigators participating in the lead-in phase evaluation and the Sponsor. Depending on experience with early cohorts of patients, not all dose levels may be explored.

Throughout the study, Nivolumab will be administered in accordance with approved labeling. Nivolumab is to be administered by intravenous infusion, using either regimen included in the approved label: 240 mg every 2 weeks (Q2W) or 480 every 4 weeks (Q4W). Guidance for adverse event management and associated Nivolumab treatment modifications are provided in the product labeling and replicated in Section 5.2 of the protocol.

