8.3.2 Cumulative Dose Administered

Dose modifications should be accounted for in the cumulative dose administered calculations below;

- Cumulative dose received for Nivolumab (mg) is defined as the total amount of Nivolumab a patient receives during the study as recorded on the Nivolumab Administration CRF forms. Nivolumab is planned to be administered at a dose of 240 mg once every 2 weeks or 480 once every 4 weeks.
- Cumulative dose received for study drug (mg) is defined as the total amount of the study drug a patient receives during the study;

The Sum of $[(\text{Last Dose Date} - \text{First Dose Date} + 1) * \text{Total Dose (mg per administration)} * \text{Dose Frequency}]$ as recorded on the Study Drug Administration CRF forms.

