8.3.4 Dose Intensity

- Relative dose intensity should apply to both Sitravatinib (Phase 2 only) and Nivolumab, from Cycle 1 Day 1, defined as:
 - For Sitravatinib, $[\text{cumulative dose received (mg)} / \text{cumulative planned dose (mg)}] * 100$, where cumulative planned dose is calculated as the starting daily dose multiplied by the study treatment duration in days.
 - For Nivolumab: $[\text{cumulative Nivolumab dose administered (mg)} / \text{cumulative planned Nivolumab dose (mg)}] * 100$, where the cumulative planned total dose is:

$$240\text{mg} \times \text{Round} \left(\frac{\text{Duration of Nivolumab (weeks)} + X}{2} \right)$$

Where X is 2 weeks for subjects who took 240mg as their last dose, and 4 weeks for subjects who took 480mg as their last dose.

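### The SAP ends nivolumab duration at the last infusion, so the same 8 weeks reads as 6.14 weeks on Q2W and 4.14 on Q4W; rounding in the dose-intensity formula makes that measure jump when infusions are late.

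*SAP*

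**What the plan says.** SAP 8.3.1 opens with "Study treatment duration will be summarized separately for each study drug and Nivolumab and is defined as" and gives one formula, (last dose date - first dose date + 1)/7, in weeks. It has no separate term for an infusion.

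SAP 8.3.2 states the two nivolumab schedules: "Nivolumab is planned to be administered at a dose of 240 mg once every 2 weeks or 480 once every 4 weeks". SAP 6.1 and Protocol 3.1 allow either one throughout the study, so one treatment arm can contain patients on both.

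SAP 8.3.4 says "Relative dose intensity should apply to both Sitravatinib (Phase 2 only) and Nivolumab". For nivolumab, the planned cumulative dose is 240 mg times Round((nivolumab duration in weeks + X)/2). The final interval enters here: "X is 2 weeks for subjects who took 240mg as their last dose, and 4 weeks for subjects who took 480mg". The SAP does not define Round.

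SAP 11.1.7.1, which sets out the exposure tables, presents relative dose intensity and compliance for sitravatinib only. It also tabulates nivolumab doses that were interrupted or delayed.

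**The concern.** First dose to last dose describes a daily capsule well, because the last dose covers one day. An infusion is followed by a planned interval of 14 or 28 days, and 8.3.1 counts one day of it. The size of the omission depends on the regimen, so when Q2W and Q4W patients are summarized together, reported nivolumab duration partly reflects which schedule was used. Set beside sitravatinib, nivolumab also appears to have been given for less time in a patient who stopped neither drug early.

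The second issue is the rounding in 8.3.4. Planned dose can only be a whole multiple of 240 mg, so a one-day difference in an infusion date can add a whole dose to the denominator. At stake is how the exposure summaries read.

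**Working it through.** The documents report no nivolumab duration or dose-intensity value, so there is no figure to reproduce. I applied the SAP's formulas to assumed schedules.

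**Inputs.** Duration formula: SAP 8.3.1. Regimens: SAP 8.3.2 and 6.1. X and the planned-dose formula: SAP 8.3.4. Round is taken as half-up.

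**Duration, 8 weeks (56 days) on schedule**

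- Q2W, infusions on Days 1, 15, 29, 43: (43 - 1 + 1)/7 = 6.14 weeks; shortfall 56 - 43 = 13 days (1.86 weeks).
- Q4W, infusions on Days 1, 29: (29 - 1 + 1)/7 = 4.14 weeks; shortfall 56 - 29 = 27 days (3.86 weeks).
- Sitravatinib daily, Days 1 to 56: 56/7 = 8.0 weeks.
- A single 480 mg infusion: 1/7 = 0.14 weeks.

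The gap between regimens does not grow with time: 22.14 against 20.14 at 24 weeks, and 50.14 against 48.14 at 52 weeks.

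Adding X to the SAP duration gives 6.14 + 2 = 8.14 and 4.14 + 4 = 8.14. Dropping the extra day as well gives 42/7 + 2 = 8.0 and 28/7 + 4 = 8.0.

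**Dose intensity on schedule**

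(6.14 + 2)/2 = (4.14 + 4)/2 = 4.07, which rounds to 4. Planned dose is 960 mg, received dose is 960 mg, and dose intensity is 100% on both regimens. If Round alone were removed, planned dose would be 240 x 4.0714 = 977.1 mg and the result 98.2%. Round is therefore absorbing the extra day.

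**Dose intensity with a delay**

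Two Q2W doses (480 mg received), second dose due on Day 15:

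| Second dose | SAP formula | Round removed only | Round and extra day removed |
|---|---|---|---|
| Day 20 (5 days late) | Round(2.43) = 2; 480/480 = 100% | 480/(240 x 2.4286) = 82.4% | 480/(120 x 4.714) = 84.8% |
| Day 21 (6 days late) | Round(2.5) = 3; 480/720 = 66.7% | 480/(240 x 2.5) = 80.0% | 480/(120 x 4.857) = 82.4% |

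One further day of delay moves the SAP value by 33 points; either unrounded version moves by about 2.4. If ties were rounded down, the step would fall at 7 days instead (raw value 2.571).

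With four Q2W doses (960 mg received), a total delay of 5 days gives 100% and 6 days gives 80%. With Round and the extra day removed, the values are 960/1045.7 = 91.8% and 960/1062.9 = 90.3%. For two Q4W doses with the same delays the results are identical, and the planned 1200 mg then equals 2.5 infusions of 480 mg.

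**The case against.** The strongest defence is that first dose to last dose is an openly stated convention and does not claim to measure weeks of drug cover. That is fair: this is a choice of definition with an awkward consequence, and the alternative has a bias of its own. A patient who receives one 480 mg infusion and dies on Day 6 would be credited with four weeks.

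A reader might infer that 8.3.1 and 8.3.4 contradict each other. They do not. Section 8.3.4 takes the duration as its input and adds X because that duration stops at the last dose.

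A reader might also infer that nivolumab exposure is understated generally. The documents do not support that. Cumulative dose (SAP 8.3.2) is unaffected, cycles started (SAP 8.3.3) would be two for 8 weeks on either regimen, and SAP 11.1.1 separately reports time from first dose to end of treatment. The shortfall is fixed, and the documents do not give the share of patients on Q4W.

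On rounding, three points stand. Round serves a purpose on schedule. Two doses is a severe example: with twelve doses received, one extra planned dose gives 12/13 = 92.3%. And if SAP 11.1.7.1 governs, nivolumab dose intensity may appear only in listings.

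Finally, the Phase 2 qualifier on sitravatinib dose intensity might be read as dropping lead-in patients treated at 120 mg. Protocol 3.2 and SAP 6.2 include lead-in patients at the chosen dose in the analysis of Phase 2 endpoints, so the qualifier need not exclude them. It merits a clarifying phrase and is not part of this error.

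**Conclusion.** The point holds as a minor one about descriptive exposure summaries. Reported nivolumab duration is short by 13 days on Q2W and 27 days on Q4W, for any length of on-schedule treatment. The rounding in 8.3.4 does no harm on schedule but distorts dose intensity when total delay is not close to a multiple of 14 days. In the two-dose example it moves from 100% to 66.7% on one day's difference, where the smooth values are 84.8% and 82.4%. Those smooth values remove both Round and the extra day, so they do not measure rounding alone.

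The figures assume the schedules shown and half-up rounding. Whether the rounding reaches a table depends on how SAP 8.3.4 and 11.1.7.1 are reconciled; the duration point does not depend on that.

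**What to change.** 1. In SAP 8.3.1, give nivolumab its own definition: duration (weeks) = (last dose date - first dose date)/7 + X, with X as already defined in 8.3.4.
2. In SAP 8.3.4, set planned nivolumab dose = 120 mg per week x that duration (240/2 = 480/4 = 120). Drop Round and the extra day together, so that on-schedule patients still score 100%.
3. Reconcile SAP 8.3.4, which applies dose intensity to nivolumab, with SAP 11.1.7.1, which presents it for sitravatinib only.
4. As a clarification, say whether the Phase 2 qualifier covers lead-in patients treated at 120 mg.

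The cost is a few SAP edits and no new data, since 8.3.4 already uses the dose dates and the last dose. SAP 4.0 provides for a final version before database lock. Reported nivolumab durations lengthen by 13 or 27 days. A patient who stops or dies soon after the last infusion is credited with the full interval, which a table footnote should state. Small shifts within the 2-day visit window will also show: for two Q2W doses, a second dose 2 days late gives 480/(120 x (16/7 + 2)) = 93.3%, and 2 days early gives 480/(120 x (12/7 + 2)) = 107.7%.

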8.3.2 Cumulative Dose Administered

Dose modifications should be accounted for in the cumulative dose administered calculations below;

- Cumulative dose received for Nivolumab (mg) is defined as the total amount of Nivolumab a patient receives during the study as recorded on the Nivolumab Administration CRF forms. Nivolumab is planned to be administered at a dose of 240 mg once every 2 weeks or 480 once every 4 weeks.
- Cumulative dose received for study drug (mg) is defined as the total amount of the study drug a patient receives during the study;

The Sum of $[(\text{Last Dose Date} - \text{First Dose Date} + 1) * \text{Total Dose (mg per administration)} * \text{Dose Frequency}]$ as recorded on the Study Drug Administration CRF forms.

8.3.3 Cycles Started

A patient is considered to have started a cycle if they received at least one dose of either study drug or Nivolumab in that cycle, per the Study Drug Administration CRF page.

8.3.4 Dose Intensity

- Relative dose intensity should apply to both Sitravatinib (Phase 2 only) and Nivolumab, from Cycle 1 Day 1, defined as:
 - For Sitravatinib, $[\text{cumulative dose received (mg)} / \text{cumulative planned dose (mg)}] * 100$, where cumulative planned dose is calculated as the starting daily dose multiplied by the study treatment duration in days.
 - For Nivolumab: $[\text{cumulative Nivolumab dose administered (mg)} / \text{cumulative planned Nivolumab dose (mg)}] * 100$, where the cumulative planned total dose is:

$$240\text{mg} \times \text{Round} \left(\frac{\text{Duration of Nivolumab (weeks)} + X}{2} \right)$$

Where X is 2 weeks for subjects who took 240mg as their last dose, and 4 weeks for subjects who took 480mg as their last dose.

8.3.5 Compliance

Compliance is only calculated for Sitravatinib (Phase 2 only), from Cycle 1 Day 1, defined as:

Compliance (%) = Cumulative Dose Received (mg) / Adjusted Cumulative Planned Dose (mg) * 100, where

Treatment Duration (Days) = Last Dose Date - First Dose Date +1, and

Adjusted Cumulative Planned Dose (mg) = Planned Dose * (Treatment Duration – Duration of Interruptions and/or Dose Reductions due to AE) + \sum (Each Planned Interruption and/or Dose Reduction (mg) * Duration of the given Planned Interruption/Reduction due to AE).

8.3.6 Days on Study Drug

Days on study drug is defined as the total number of days that a patient received treatment, after subtracting for interruptions or drug missed, that is:

- The $[(\text{Last Dose Date} - \text{First Dose Date}) \text{ captured on the Study Drug Administration CRF page} - \text{number of days with 0 mg dose} + 1]$.

8.4 Safety Variables

With regard to safety summaries, the term “on-treatment” is the period from first dose until either last dose + 28 days or the start of anti-cancer therapy, whichever is earlier.

AEs, laboratory values and ECGs will be graded according to the NCI CTCAE v4.03 (see Section 13.0 for link to the criteria), ECGs will also be graded according to International Conference on Harmonisation (ICH) E14.

8.4.1 Adverse Events

8.4.1.1 Treatment-Emergent AEs (TEAEs)

TEAEs are those that first occur or increase in severity after the first dose of study treatment and not more than 28 days after the last dose of study treatment and prior to the initiation of subsequent anti-cancer therapy. Any ongoing TEAE (or any baseline sign/symptom recorded as part of Medical History) that changes in attribution or increases in severity is captured as a new AE.

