8.2 Adverse Events

An adverse event (AE) is any reaction, side effect or other undesirable medical event that occurs during participation in a clinical trial, regardless of treatment group or suspected causal relationship to study treatment. A treatment emergent AE (TEAE) is an AE that occurs after the first dose of any study treatment or any preexisting condition that increases in severity after the first dose of study treatment.

All observed or volunteered AEs will be recorded in source documents and reported in the CRF. The best available medical terminology should be used to describe AEs in source documents and CRFs. Terms describing the diagnosis are preferred over individual signs and symptoms of the diagnosis. If determination of the diagnosis is delayed, record signs and symptoms and add the diagnosis as an AE when available; follow all recorded AEs to resolution. Examples of AEs include but are not limited to:

- Signs or symptoms of co-morbidity, illness, or toxicity of study treatment;
- Signs or symptoms of worsening malignancy under study (disease progression assessed by measurement of malignant lesions should not be reported as an AE).
- Laboratory abnormalities (see Section 8.2.1 for guidance for reporting in CRF);
- Hypersensitivity;
- Drug abuse, dependency, overdose, withdrawal or misuse;
- Signs or symptoms of drug interactions;
- Extravasation;
- Exposure during pregnancy or via breastfeeding;
- Medication error; or
- Occupational exposure.

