8.4 Reporting of SAEs and AEs

8.4.1 Reporting Period

The active reporting period for SAEs begins from the time that the patient provides informed consent (i.e., prior to undergoing any study-specific procedure or assessment) and continues until 28 days post last administration of either therapy. All SAEs will be followed until the event has resolved or stabilized to a chronic condition, whichever is later. Death must be reported if it occurs during the active reporting period for SAEs regardless of whether a subsequent anticancer therapy is administered. Serious adverse events occurring to a patient after the active reporting period has ended should be reported to the Sponsor if the Investigator becomes aware of them and if the Investigator assesses at least a reasonable possibility of being related to study drug.

The reporting period for non-serious AEs begins from the day of first dose of study treatment and continues until at least 28 days after last administration of study treatment and/or until recovery from all acute toxicities associated with the drug administration to a chronic condition, whichever is later. If a patient begins a subsequent anticancer therapy, the AE reporting period ends at the time the new treatment is started.

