9.1.2 Imputation of Partial Subsequent Anti-Cancer Therapy Dates

The following rules will be applied to impute missing subsequent anti-cancer therapy dates.

Missing Day Only

- If the month and year of the incomplete date are the same as the month and year of the last dose date, then the last dose date + 1 will be assigned to the missing day.
- If the month and year of the incomplete date are after the month and year of the last dose date, then the first day of the month will be assigned to the missing day.

Missing Month Only

- The day will be set as missing and treated as missing Day and Month.

Missing Day and Month

- If the year of the incomplete date is the same as the year of the last dose date, then the last dose date + 1 will be assigned to the missing day and month.
- If the year of the incomplete date is after the year of the last dose date, then January 01 will be assigned to the missing fields.

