11.0 Planned Analysis

PK sub-study patients will be excluded from any main study summaries and will be presented in PK sub-study specific summaries only. Screen Failures will be summarized in a Screen Failure table, but otherwise excluded from all tables and listings. Listings will include all relevant derived variables.

All data collected during this study will be displayed in data listings, unless otherwise specified. Data listings will be presented separately for enrolled patients in the main study and those in the PK sub-studies.

Descriptive statistics (mean, median, standard deviations [STD] or standard error, first quartile [Q1], third quartile [Q3], minimum and maximum values) for continuous variables will be presented. Mean and median will be presented to 1 decimal more than original data. STD will be presented to 2 decimals more than original data. Minimum and maximum values will match the decimal points in the original data. For categorical variables, summary measures will include the frequency and percentage (with 1 decimal place) of patients in each category.

Safety summaries will be presented for assessments on-treatment (as defined in Section 8.4) and will include patients from both the safety lead-in and phase 2 parts of the study. Efficacy summaries will be presented for assessments on-study (defined in Section 8.2) and will include patients receiving the recommended phase 2 dose (120mg QD) only. All tables will be presented by treatment arm and strata.

Unless otherwise noted, missing data will not be imputed or carried forward.

All data summaries and tabulations will be prepared with SAS® v9.4 or higher.

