11.1.7.3 Serious Adverse Events (SAEs) and Deaths

The following summaries of treatment emergent SAEs, including TEAEs that lead to death, will be presented by SOC and PT for the Sitravatinib plus Nivolumab treatment arm, using the Safety Population:

- Any Treatment-Emergent SAEs
- Any Treatment-Related Treatment-Emergent SAEs
- Any Nivolumab-Related Treatment-Emergent SAEs
- Any Sitravatinib-Related Treatment-Emergent SAEs
- Any TEAE with an outcome of death

In addition to the SOC and PT summaries, the following summaries will also be presented by PT only for the Sitravatinib plus Nivolumab treatment arm

- Any Treatment-Emergent SAEs
- Any Treatment-Related Treatment-Emergent SAEs

All treatment emergent SAEs and TEAEs with an outcome of death will be listed.

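### The SAE and fatal-AE tables stop at new anti-cancer therapy, or at the day after last dose when its date is partial, although the protocol collects these events to day 28

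*SAP*

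**What the plan says.** **SAP.** Section 8.4 defines on-treatment, for safety summaries, as "the period from first dose until either last dose + 28 days or the start of anti-cancer therapy, whichever is earlier", and section 11.0 applies that definition to the safety summaries. Section 8.4.1.1 sets the same end for treatment-emergent events: "not more than 28 days after the last dose of study treatment and prior to the initiation of subsequent anti-cancer therapy". Neither section separates serious or fatal events from the rest. In section 11.1.7.3 every table of SAEs and of AEs with fatal outcome is a treatment-emergent table, and the listing it names is too: "All treatment emergent SAEs and TEAEs with an outcome of death will be listed".

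Section 9.1.2 handles partial dates of subsequent therapy. If only the year is known and it is the year of the last dose, "then the last dose date + 1 will be assigned to the missing day and month". The same date is assigned if month and year are known and both match the last dose.

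**Protocol.** Section 8.4.1 collects SAEs from consent to 28 days after the last administration of either therapy. On deaths it says: "Death must be reported if it occurs during the active reporting period for SAEs regardless of whether a subsequent anticancer therapy is administered". For later events it says: "Serious adverse events occurring to a patient after the active reporting period has ended should be reported to the Sponsor", provided the investigator learns of them and sees a reasonable possibility of a relation to study drug. New therapy ends reporting only in the paragraph on non-serious AEs. Section 8.2 sets no end to the treatment-emergent period: "A treatment emergent AE (TEAE) is an AE that occurs after the first dose of any study treatment", or a pre-existing condition that worsens after that dose.

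**The concern.** Safety is a secondary endpoint, and the main safety result will be the incidence tables for the sitravatinib arm. Two things can make the SAE and fatal-AE counts too low.

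First, sites must report an SAE or death that occurs within 28 days of the last dose but after new therapy has started. Under the SAP it then enters no SAE or fatal-AE table.

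Second, the date rule in SAP 9.1.2 can remove an event that happened before new therapy began, because it gives the new therapy the earliest post-dose date whenever the record is incomplete. That is not a choice about attribution; it is a misclassification.

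The protocol itself notes, in section 1.7.3.3.8, that immune-mediated reactions may occur after nivolumab is stopped, so post-dose events are to be expected.

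**Working it through.** The plan states no figure for this point, so there is none to reproduce. The check sets the windows side by side and then counts calendar days.

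**Windows by type of event**

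| Event | Protocol 8.4.1 collection | SAP table window |
|---|---|---|
| Non-serious AE | stops at new therapy | stops at new therapy or day 28: agrees once new therapy has a known date |
| Non-fatal SAE | to day 28, no stop at new therapy stated | stops at new therapy or day 28 |
| Death | to day 28, explicitly regardless of new therapy | fatal AE stops at new therapy or day 28 |
| Related SAE after day 28 | to be reported if the investigator becomes aware | outside the window because of the 28-day limit |

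SAP 8.4.1.2 restates the SAE collection period as at least 28 days after the last administration, with no cut at new therapy for new events. No table in 11.1.7.3 uses that period. SAP 4.1 lists other changes from the protocol but not this one.

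**Days that qualify.** Let new therapy start k days after the last dose. An onset on post-dose day 1 to 28 qualifies only if it falls before day k, so the number of qualifying days is min(28, k − 1).

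- No new therapy, or k ≥ 29: 28 days.
- k = 28, 21, 14, 7: 27, 20, 13 and 6 days.
- Partial date imputed under SAP 9.1.2, k = 1: 0 days.

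Days wrongly lost through imputation are therefore min(28, true k − 1), which runs from 0 to 28.

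**Example: last dose 10 March, so day 28 is 7 April.**

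- Only the year recorded. Compatible dates run from 11 March to 31 December: 21 + 275 = 296 dates. Of these, 296 − 28 = 268 fall after day 28, and 268/296 = 91%. On those dates no cut was due, yet all 28 days are lost.
- March recorded, day missing. The latest true start is 31 March, k = 21, so at most 20 days are wrongly lost.

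**Average over last-dose dates.** Assume the true start is uniform over the compatible dates, and average over all last-dose dates in a non-leap year. The mean wrongful loss is about 7 days when only the day is missing and about 24 days when day and month are missing. The maximum is 28 in both cases.

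**One event.** Same patient, only the year recorded, SAE on 25 March. It is wrongly removed if therapy really began after 25 March; 11 to 25 March is 15 dates. The chance depends on the assumed spread of the true start:

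- uniform to 31 December: 1 − 15/296 = 95%;
- uniform over 61 days, about one 2-month follow-up interval: 1 − 15/61 = 75%;
- uniform over 28 days: 1 − 15/28 = 46%.

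The documents do not say which spread is realistic.

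**The case against.** The strongest reply is that a reporting duty is not a promise to tabulate. Protocol section 9 lets the SAP modify planned analyses, with an amendment needed only for major changes to the primary endpoint. Ending the window at new therapy also keeps the next drug's toxicity out of the tables. This stands as a defence of choosing a cut, but not of leaving it out of SAP 4.1, and it does not touch the imputation, which can remove events that came before the new drug.

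Several stronger readings are tempting, and the documents do not support them.

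- *The events vanish from all safety output.* SAP 11.1.1 tabulates deaths with cause and sets no treatment-emergent limit, SAP 11.1.7.6 lists causes of death, and SAP 11.0 lists all collected data unless otherwise specified.
- *Late related SAEs are lost because of new therapy.* The 28-day limit excludes them, with or without new therapy.
- *Immune-related events drop out as well.* SAP 8.4.2 identifies them by a CRF flag with no time window, and SAP 11.1.7.2 keeps a separate listing. Only the general on-treatment clause in 11.0 could restrict the summary.
- *Every matching partial date costs the full 28 days.* When the month is known the wrongful loss is usually much smaller.
- *All the date rules push counts down.* SAP 9.1.1 places partial AE start dates in the first-dose month, or in a later month, at the earliest day it allows, which favours counting them.
- *The first month off drug is when late toxicity appears.* No passage says this; the protocol says only that reactions may occur after discontinuation.

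For non-fatal SAEs, collection after new therapy follows from an unqualified 28-day period; only deaths have explicit wording.

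**Conclusion.** The concern holds in a limited form. The SAE and fatal-AE incidence tables are cut at new therapy, the protocol's collection rule for these events is not, and SAP 4.1 is silent. With complete dates, the events lost are those between the true start of new therapy and day 28. With a partial date matching the last dose, all 28 post-dose days are lost, and 0 to 28 of those are lost wrongly.

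How many events this moves cannot be computed: the documents give neither the rate of post-dose SAEs nor the number of partial new-therapy dates. The averages and the 46% to 95% range rest on assumed uniform start dates and show only how sensitive one patient's classification is. The absence of a table for related SAEs after day 28 is a separate and lesser matter; their reporting depends on the investigator becoming aware of them, so a listing is enough.

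**What to change.** 1. **SAP 8.4, 8.4.1.1 and 9.1.2.** For safety derivations, treat an AE within 28 days of the last dose as treatment-emergent unless the known part of the new-therapy date shows that therapy began first. Do not use the day after last dose for this purpose.
2. **SAP 11.1.7.3.** Present the SAE and fatal-AE tables from first dose to 28 days after the last dose regardless of new therapy. Flag events that began after new therapy, and mark the order as undetermined where a partial date leaves it open.
3. **SAP 11.1.7.3.** State that SAEs after day 28 judged related are included in a listing.
4. **SAP 4.1.** Record how the treatment-emergent definition departs from protocol 8.2 and 8.4.1.

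The cost is SAP wording and a small programming change, using data the protocol already collects. Reported SAE and fatal-AE incidence may rise slightly and include a few events confounded by the next therapy; the flag makes these visible.
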